# COVER PAGE FOR PROTOCOL AND STATISTICAL ANALYSIS PLAN

**Official Study Title: Effect of Dapagliflozin on Hepatic and Renal Glucose Metabolism Subjects**

**NCT number: NCT02981966**

**IRB Approval Date: 10/18/19**

**Unique Protocol ID: HSC20160596H**

**Effect of Dapagliflozin on Hepatic and Renal Glucose Metabolism Subjects**

Two groups of subjects (age = 18-70 years; BMI = 21-45 kg/m^2; males or females) will participate: (i) 24 healthy NGT individuals, and (ii) 24 T2DM subjects according to the ADA criteria. NGT and diabetic subjects will be matched for age, sex and BMI. Diabetic subjects must be on a stable dose (more than 3 months) of monotherapy or combination therapy with metformin and/or a sulfonylurea and have HbA1c <8.0%. Subjects taking drugs known to affect glucose metabolism (other than metformin and sulfonylurea) will be excluded. Other than diabetes, subjects must be in good general health as determined by physical exam, medical history, blood chemistries, CBC, TSH, T4, EKG and urinalysis. Only subjects whose body weight has been stable ( $\pm$  3 lbs) over the preceding three months and who do not participate in an excessively heavy exercise program will be included. Individuals with evidence of proliferative diabetic retinopathy, plasma creatinine >1.4 females or >1.5 males, or 24-hour urine albumin excretion > 300 mg will be excluded. Diabetic subjects will be recruited from the Texas Diabetes Institute (TDI) in San Antonio (Deputy Director = [name]). TDI is the largest institute in the United States that provides comprehensive care for  $\sim$  10,000 unduplicated T2DM patients. Therefore, we do not anticipate any problem in recruiting the required number of patients for this study. NGT subjects will be recruited from volunteers who have participated in prior studies.

Following a screening visit to determine eligibility, NGT subjects will receive a 75-gram OGTT to confirm glucose tolerance status. In all subjects, the rate of whole body (liver plus kidney) and renal glucose (renal vein catheterization with 3-H-glucose) production will be measured before and after dapagliflozin or placebo. T2DM and NGT subjects will be randomized 2:1 to receive dapagliflozin (n=16) or placebo (n=8).

The reason for including both NGT and T2DM subjects is provided below. In NGT subjects who ingest an SGLT2 inhibitor, urinary glucose excretion promptly increases and amounts to  $\sim$ 72 grams/day (58,59), yet the fasting plasma glucose concentration does not change. This means that endogenous glucose production (kidney plus liver) must increase to precisely match the rate of renal glucose excretion. Therefore, from the quantitative standpoint this will provide the greatest stimulus to augment EGP and, thus, the greatest ability to define the role of the kidney in the increase in EGP. Because, in T2DM subjects, EGP turns on long before the fasting plasma glucose concentrations return to normal, the increase in EGP (and, therefore, any increase in renal glucose production) will be less than in the NGT individuals. Nonetheless, we are very interested in the contribution of the kidney to the increase in EGP in T2DM subjects following dapagliflozin. Therefore, we have included both NGT and T2DM subjects.

**Visit 1: Screening.** Medical history will be obtained. EKG and physical exam will be performed. Blood will be drawn for FPG, routine blood chemistries, CBC, PT, lipid profile, coagulation tests, HbA1c, and thyroid function. Urinalysis, albumin/creatinine ratio and pregnancy test will be performed. NGT subjects will receive 75-gram OGTT to confirm their glucose tolerance status; plasma glucose, insulin, glucagon and C-peptide conc will be measured before (-30, -15, 0 min) and every 15 min for two hours after glucose ingestion. T2DM subjects will not receive OGTT. An interim visit might be needed for pre-cath evaluation and drawing of coagulation tests.

**Visit 2:** The rate of whole body (liver plus kidney) and renal glucose production will be measured with 3-H-glucose in combination with renal vein catheterization. On admission date, subjects will report to the CRC at 6 AM after a 10 hour overnight fast. At 7 AM a catheter will be placed into an antecubital vein and a prime (40 uCi x FPG/100)-continuous (0.4 uCi) infusion of [3-H]-glucose will be started and continued until 2 PM (4 hours after dapagliflozin or placebo administration). At 8 AM subjects will transfer to cath lab from BRU for renal vein catheter insertion via the femoral vein, under fluoroscopy, or jugular vein, guided by ultrasound. The determination for using the jugular or femoral vein will be under the expertise of [name] (examples: body build, accessibility to femoral vein, circulatory system anatomy, safety concerns with using the femoral vein). Catheter placement will be confirmed by injection of a small amount of contrast material. The renal catheter will be continuously infused with a small amount of saline to maintain its patency. Additionally, a second catheter will be placed in the radial artery by [name] for withdrawal of arterial blood. After finishing these procedures the subjects will be transferred back to the BRU. At 7 AM a prime (8 mg/kg)-continuous (12 mg/min) infusion of para-aminohippuric acid (PAH) will be started for determination of renal blood flow. After 3 hours of tracer equilibration time in T2DM (2 hours in NGT subjects) blood samples will be drawn from the renal vein and arterial catheters at -30,-20, -10,-5 and 0 (time zero is drug [dapagliflozin or placebo] ingestion time) minutes. At 10 AM (time zero), subjects will receive dapagliflozin (10 mg) or placebo and blood samples will be obtained from the radial arterial and renal vein catheters every 20 minutes from 10 AM to 2 PM. Plasma glucose, insulin, C-peptide, glucagon, cortisol, growth hormone, catecholamine, and PAH conc and [3-H]-glucose specific activity will be measured in blood samples drawn from arterial catheter. The plasma glucose conc and [3-H]-glucose sp act will be measured from the renal sample. Additionally, 3 arterial and 3 venous samples at baseline and at the end of study will be drawn to measure PO2 and O2 sat, with an iSTAT handheld analyzer. We will also draw blood

to monitor kidney function. Urine will be collected from 7 to 10 AM and from 10 AM to 2 PM. Urinary volume and urinary glucose and PAH conc will be measured to obtain urinary glucose excretion and to measure renal plasma flow (PAH clearance). The study will end at 2 PM and there will be a 3hr observation period before subjects are discharged at 5 PM. Subjects will be asked to collect a 24- Hour Urine Collection to determine creatinine excretion after either Visit 1 or Visit 2.

Renal oxygenation plays a key role in the pathophysiology of chronic kidney diseases progression. To date, the validated methods for quantitatively measuring kidney oxygenation in humans use invasive catheters/biopsy. Direct arterial-venous kidney oxygenation measurement is available only at a small number of research sites. The availability of a clinically practical oxygenation measurement will find immediate applications in many kidney hypoxic diseases including diabetic nephropathy, kidney artery stenosis, and acute kidney injury.

Visit 2B: Subjects will be asked to come back to BRU for follow up and recovery status within 7 days after Visit 2.

**Visit 3:** Renal (Kidney) MRI: A renal MRI will be performed on subjects for the measurement of kidney size, and whole-organ metabolic rate of oxygen (MRO2). Before entering the MRI scanner, the subject will be surveyed for magnetic articles on his/her person or clothing and briefed regarding the safety requirements of the MRI study. This MRI procedure is entirely non-invasive.

**Data Analysis and Statistical Methods:** *The primary end point* is the difference in EGP (total, renal and hepatic) (see below) during the last hour of study (180-240 min) between subjects receiving dapagliflozin versus placebo. The whole body rate of EGP will be calculated from the 3-H-glucose infusion as previously described (10). Under steady-state postabsorptive conditions, the basal rate of whole body endogenous glucose appearance (Ra = bEGP) equals 3-H-glucose infusion rate divided by steady state plasma tritiated glucose specific activity. After drug administration, non-steady conditions for 3-H-glucose specific activity prevail and the rate whole body of glucose appearance (Ra) is calculated from Steele's equation (57). Ra equals the rate of EGP after drug administration. Ra will be calculated for each time point after dapagliflozin administration and will be plotted versus time and compared to Ra in placebo-treated group.

**Renal Glucose Production** (RGP) will be calculated as previously described (27). Renal plasma flow (RPF) is calculated as the clearance of PAH; renal blood flow (RBF) is calculated as: RBF = RPF/(1-hematocrit). Net Renal Glucose Balance = RBF X (Artglu-RVglu). Renal glucose fractional extraction (FE) is calculated from tritiated glucose radioactivity as: FE = (Adpm-RVdpm)/Artdpm and Renal Glucose Uptake = RBF X FE X [Glucose]art. From the following equation: Net Renal Glucose Balance = Renal Glucose Uptake - Renal Glucose Production, one can calculate Renal Glucose Production (RGP) as: RGP = (RBF x FE x [Glu]Art - (RBF x [GluArt-RV])). HGP is calculated as Ra(total) - RGP. The effect of dapagliflozin versus placebo on RGP and HGP will be calculated as the difference in each parameter (RGP and HGP) at each time point minus the mean value before drug administration.

Values will be presented as mean  $\pm$  SD. The change in EGP and RGP after dapagliflozin and placebo will be compared in the two groups (NGT + T2DM) with repeated measures ANOVA with time and treatment group as factors. Only subjects who complete the entire protocol will be analyzed.

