#### **Anticipated Results and Potential Limitations:**

The results of the present study will identify the organ, liver and/or kidney, responsible for the increase in EGP following dapagliflozin administration. Our published results (10) demonstrate that the decrease in FPG concentration (43 mg/dl) following two weeks of dapagliflozin treatment in T2DM subjects was associated with an increase in EGP (0.45 mg/kg.min). Because inhibition of SGLT2 in healthy NGT individuals is not accompanied with a significant change in the FPG concentration (58,59), we anticipate that the increase in EGP in NGT individuals will be even greater than in T2DM individuals. Based on the amount of glucosuria produced with SGLT2 inhibitors in NGT individuals (72 grams/day) (58,59), in order to compensate for the total renal glucose loss, we anticipate that the rate of EGP will increase following dapagliflozin by  $\sim$ 0.7 mg/kg.min above baseline. The contribution of the kidney to whole body glucose production is  $\sim$ 20-25% (26). Since whole body EGP under basal conditions is  $\sim$ 2 mg/kg.min (2), the contribution of renal glucose release to EGP is  $\sim$ 0.4 mg/kg.min. Thus, the kidney has to double, or even triple, its rate of glucose production in NGT individuals in order to account for the increase in total EGP triggered by glucosuria. Moreover, published results indicate that renal glucose production is not responsive to an increase in plasma glucagon concentration (29,30). In contrast, insulin and glucagon are powerful regulators of HGP (6,17,18). Therefore, we anticipated that, at least in part,

an increase in HGP secondary to the rise in plasma glucagon concentration and decrease in plasma insulin concentration in response to dapagliflozin-induced glucosuria (Figure 1) will account for the majority of increase in EGP in both NGT and T2DM subjects (see discussion below). However, it is possible that local effects of SGLT2 inhibition stimulate renal glucose production (60,61) without the need for a hormonal signal. Measurement of renal glucose production will provide a direct and definitive answer to the contribution of the kidney to the observed increase in total EGP following SLGT2 inhibition.

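### The renal glucose production formula multiplies whole-blood flow by plasma glucose with no conversion written out, so the estimated kidney/liver split depends on an unstated red-cell glucose ratio

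*Combined protocol and SAP*

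**What the plan says.** The Renal Glucose Production paragraph of the combined protocol and SAP defines flow as follows: "Renal plasma flow (RPF) is calculated as the clearance of PAH; renal blood flow (RBF) is calculated as: RBF = RPF/(1-hematocrit". This whole-blood flow (RBF) then enters both terms of the formula. Net balance is RBF times the arterial minus renal-vein glucose difference. Uptake is RBF times tracer fractional extraction (FE) times arterial glucose. RGP is uptake minus net balance, and "HGP is calculated as Ra(total) - RGP".

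That paragraph does not say whether glucose is in plasma or whole blood. The Visit 2 section does. The arterial list opens "Plasma glucose, insulin, C-peptide, glucagon, cortisol, growth hormone, catecholamine, and PAH conc", and for the other site plasma glucose and tracer "sp act will be measured from the renal sample". Neither section describes a whole-blood glucose assay or a conversion factor. The method is attributed to reference 27, which is not reproduced. The only hematocrit measurement described is at screening (Risk Benefit, item a).

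Total, renal and hepatic EGP together form the primary end point, compared "during the last hour of study (180-240 min) between subjects receiving dapagliflozin versus placebo". The Anticipated Results section says that measuring RGP "will provide a direct and definitive answer to the contribution of the kidney".

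**The concern.** Whole-blood flow should be paired with whole-blood glucose. Pairing it with plasma glucose is exact only if red cells carry glucose at the plasma concentration, an assumption the plan does not state. If they carry less, the written equations credit the kidney with too much glucose. Because HGP is found by subtraction, the liver is debited by the same amount.

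The estimated split between the two organs is at stake. Both components belong to the primary end point, and the plan presents the kidney's contribution as the question the study will answer. Whether RGP responds to the drug at all is not at stake, as the working shows.

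**Working it through.** **Inputs from the documents.** Design effect on RGP 0.35 mg/kg.min, half of an EGP rise of 0.70; SD 0.34; 32 versus 16 subjects; alpha 0.05; stated power 90% (Sample Size Calculation). Basal EGP about 2 mg/kg.min with a renal share of about 20–25% (Anticipated Results). Hematocrit entry limit 34% (Risk Benefit, item a).

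**Assumed.** Hematocrit values of 40% and 45%; r from 0.7 to 1, equal in artery and vein; a two-sided test. The documents give no r and no renal PAH extraction.

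**Step 1: the plan's own figures.** SE = 0.34 × √(1/32 + 1/16) = 0.104. A two-sided t-test for a difference of 0.35 on 46 df has 90.8% power, which matches the stated 90%. Basal RGP = 20% × 2 = 0.4 mg/kg.min also reproduces.

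**Step 2: the factor.** As written, with plasma values A (arterial) and V (renal vein):

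RGP_written = [RPF/(1 − Hct)] × [FE × A − (A − V)].

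Whole-blood glucose = plasma glucose × (1 − Hct(1 − r)). FE is a ratio, so the factor cancels from it. It multiplies A and V alike and comes out of the bracket:

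RGP_written / RGP_true = 1/(1 − Hct(1 − r)).

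| r | Hct 34% | Hct 40% | Hct 45% |
|---|---|---|---|
| 1.0 | 1.000 | 1.000 | 1.000 |
| 0.9 | 1.035 | 1.042 | 1.047 |
| 0.8 | 1.073 | 1.087 | 1.099 |
| 0.7 | 1.114 | 1.136 | 1.156 |

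**Step 3: the split.** HGP_written = Ra − RGP_written, so HGP moves by the same mg/kg.min with the opposite sign. Take a true 0.35 renal and 0.35 hepatic rise, Hct 40%, r = 0.7:

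- RGP reads 0.35/0.88 = 0.398.
- HGP reads 0.70 − 0.398 = 0.302.
- The renal share reads 0.398/0.70 = 57% instead of 50%.

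At r = 0.9 and the same hematocrit, the readings are 0.365 and 0.335 (52%). At baseline, a true 0.40 of 2.0 reads 0.455, a share of 22.7% instead of 20%.

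**Step 4: what does not change.** Total EGP comes from the systemic tracer alone. A common factor scales the RGP effect and its SD together, so the test and its 90.8% power stay the same. If the true RGP change is zero, zero is what gets scaled, and the HGP change is unbiased. These statements need a factor that is the same in both arms and stable after dosing.

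**Step 5: size against precision.** In the design scenario the shift is 0.398 − 0.35 = 0.048, or 0.048/0.104 = 0.46 SE. At Hct 45%, r = 0.7 it is 0.405 − 0.35 = 0.055, or about 0.5 SE. The shift grows with the true RGP change: if all 0.70 came from the kidney, it would be 0.70/0.88 − 0.70 = 0.095 at Hct 40%, r = 0.7, still under one SE, and 0.70/0.865 − 0.70 = 0.109 at Hct 45%, about one SE.

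**Step 6: PAH extraction.** PAH clearance equals E × RPF, where E is the fraction of PAH the kidney extracts. The Visit 2 section does not list PAH among the renal-vein assays. If E < 1, flow is understated, and the net factor is E/(1 − Hct(1 − r)). At Hct 40%, r = 0.7:

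- E = 1: +13.6%.
- E = 0.95: 0.95/0.88 = 1.08, so +8%; correcting for r alone leaves −5%.
- E = 0.90: 0.90/0.88 = 1.02, so +2%; correcting for r alone leaves −10%.
- E = 0.88: the two errors cancel.

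**The case against.** The strongest objection concerns direction. A reader might infer that the plan overstates RGP. Step 6 shows that this does not follow: the documents give neither r nor E, the two act in opposite directions, and correcting only one can increase the error. This stands. The scaling by 1/(1 − Hct(1 − r)) is the effect of the unit mismatch alone, not the net error.

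A reader might also infer that the trial's RGP values will be miscalculated. The plan defers to reference 27, and converting to whole-blood flow would make sense if that method uses blood glucose. The text may be a shortened description. That also stands. However, the paragraph writes its equations out in full, so a conversion, if there is one, belongs there.

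A third tempting reading is that the mismatch could turn a hepatic majority into a renal one. No section sets a test or decision rule at a 50% kidney share. The 0.35 figure is the difference the study is powered to detect, and the Anticipated Results section expects the liver to dominate. The 57% reading is therefore an illustration, not a reversed finding.

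Finally, the shift is small beside sampling error. In the design scenario the 95% interval for RGP is about 0.35 ± 0.21, or 0.14 to 0.56. The plan also concedes that an undetectable renal change would not exclude a small renal contribution. Both facts limit the importance of the point. They do not remove it, because a scale error in the estimates does not average out as subjects are added.

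**Conclusion.** The point holds as a defect in the formula as written. Whole-blood flow is paired with plasma glucose and no conversion is shown, which is exact only at r = 1. For assumed hematocrits of 34–45%, this alone scales RGP by about +3.5% to +5% at r = 0.9, +7% to +10% at r = 0.8 and +11% to +16% at r = 0.7, with an equal and opposite shift in HGP.

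Only the estimated kidney/liver split is affected, by less than one SE at the plan's design effect. Total EGP, the RGP test and its power stand. The net direction of error in RGP stays open because PAH extraction is unknown. The conclusion rests on assumed values of r, on r being equal in artery and vein, and on reference 27 not already supplying the step. It is worth correcting because two components of the primary end point depend on it, but it does not threaten the trial's main comparison.

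**What to change.** In the Renal Glucose Production paragraph:

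1. Pair like with like. Use RBF with whole-blood glucose, computed as plasma glucose × (1 − Hct(1 − r)), with a sourced r and a named hematocrit sample. If reference 27 already converts, write its conversion out.
2. As a sensitivity analysis, report RGP, HGP and the kidney share of the EGP rise over a sourced range of r, including r = 1 (the present formula), and over a sourced range of PAH extraction. Varying both avoids correcting one error and exposing the other.

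This needs no new samples or procedures. It rescales data already planned and can be applied to subjects already studied. The costs are that r and E must be sourced, and that reported RGP may change by several percent.

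Whole-blood assay is not needed. If it were chosen, it should cover every time point at which RGP is computed: (5 baseline + 12 post-drug) × 2 sites = 34 assays per subject, or 34 × 48 = 1,632 in total.

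### Uncorrected PAH clearance multiplies renal glucose production by an unmeasured extraction ratio and books the remainder to the liver; the net direction of bias is not settled

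*Combined protocol and SAP*

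**What the plan says.** In Data Analysis and Statistical Methods, under Renal Glucose Production: "Renal plasma flow (RPF) is calculated as the clearance of PAH". Renal blood flow (RBF) is then RPF divided by one minus the hematocrit, both terms of RGP are multiplied by RBF, and "HGP is calculated as Ra(total) - RGP". Ra comes from the tracer and does not use RBF.

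The Visit 2 text gives the source of the clearance: "Urinary volume and urinary glucose and PAH conc will be measured to obtain urinary glucose excretion and to measure renal plasma flow (PAH clearance"). There are two collection periods: "Urine will be collected from 7 to 10 AM and from 10 AM to 2 PM".

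Visit 2 also assigns the assays. For the artery, at the end of a longer list: "PAH conc and [3- 3 H]-glucose specific activity will be measured in blood samples drawn from arterial catheter". For the renal vein: "The plasma glucose conc and [3- 3 H]-glucose sp act will be measured from the renal sample". The renal vein list does not include PAH, although blood is drawn there at the same times as from the artery. No PAH extraction ratio, measured or assumed, appears anywhere.

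Renal and hepatic EGP are both named in the primary end point. The Anticipated Results section says the study will show which organ supplies the extra glucose, and expects it to be mostly the liver.

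**The concern.** Urinary clearance of PAH measures the plasma flow that is completely cleared. It equals total renal plasma flow only when no PAH leaves in the renal vein. If some does, the calculated flow is low, and calculated RGP is low by the same factor.

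A proportional error of this kind might be thought harmless, since it applies in both arms. For this trial it is not, because HGP is found by subtraction from a total that is not scaled. Whatever is lost from the kidney is added to the liver, inside the dapagliflozin-placebo contrast. Randomization does not remove it, and the kidney/liver split is what the trial is meant to measure.

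**Working it through.** **The plan's own figure.** Sample Size Calculation claims 90% power for a 0.35 (SD 0.34) mg/kg.min rise in RGP with 32 versus 16 subjects at alpha 0.05. A two-sided two-sample t test gives 90.8% (normal approximation 92.0%), so the figure reproduces. The standard error is 0.34 × √(1/32 + 1/16) = 0.104.

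**Effect of extraction.** Let A and RV be arterial and renal vein PAH, and E = (A − RV)/A, which cannot exceed 1.

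1. At steady state, urinary PAH excretion = RPF × (A − RV).
2. Clearance = excretion/A = RPF × E.
3. RGP = RBF × [FE × Glu(art) − (Glu(art) − Glu(RV))] is linear in RBF, and RBF is linear in RPF. So calculated RGP = E × true RGP.
4. Calculated HGP = Ra − E × true RGP = true HGP + (1 − E) × true RGP.

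**Numbers.** From the documents: basal RGP about 0.40 mg/kg.min; target RGP rise 0.35, half of a 0.70 EGP rise. E is not given, so 0.80 to 0.95 is an assumption. Calculated RGP rise = 0.35 × E; calculated HGP rise = 0.70 − 0.35 × E.

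| E | RGP rise | HGP rise | Kidney/liver share |
|---|---|---|---|
| 1.00 | 0.3500 | 0.3500 | 50/50 |
| 0.95 | 0.3325 | 0.3675 | 47.5/52.5 |
| 0.90 | 0.3150 | 0.3850 | 45/55 |
| 0.85 | 0.2975 | 0.4025 | 42.5/57.5 |
| 0.80 | 0.2800 | 0.4200 | 40/60 |

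If the whole 0.70 rise were renal, a false liver rise of (1 − E) × 0.70 would appear: 0.035 at E = 0.95, 0.14 at E = 0.80.

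**Power.** With constant E, the mean and SD of RGP shrink together and power stays at 90.8%. If the SD of calculated RGP were nevertheless 0.34, power would be 87.8% (E = 0.95), 84.2% (0.90), 79.9% (0.85) or 75.0% (0.80).

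**If E changes after drug.** With E going from 0.90 to 0.80, a true rise from 0.40 to 0.75 reads as 0.80 × 0.75 − 0.90 × 0.40 = 0.24. A true zero change reads as 0.80 × 0.40 − 0.90 × 0.40 = −0.04. With E going from 0.90 to 0.95, the true zero reads as +0.02.

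**The opposing error.** Glucose is measured in plasma but multiplied by whole-blood flow. If whole-blood glucose is f times plasma glucose, with the same f in artery and vein, then calculated/true RGP = E/f. The documents give no f; assume 0.85 to 0.95. The ratio then runs from 0.80/0.95 = 0.84 to 0.95/0.85 = 1.12, and equals 1 when E = f, for example both 0.90. Correcting E alone would leave 1/f, that is 1.05 to 1.18.

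**The case against.** - **The size rests on an outside quantity.** This stands. The documents never say that PAH extraction is incomplete. The algebra alone shows only that this route cannot overstate RGP.
- **Net direction.** A reader might infer that the trial as a whole will understate the kidney and so favour the answer the investigators expect. The documents do not support that: the plasma/whole-blood mismatch may push RGP up by as much or more. The shift from E is also proportional to the true renal effect, so it vanishes if the kidney contributes nothing to the rise.
- **The planned tests survive.** This stands for constant E. A reader might infer that the sample size or the test of no renal effect is wrong; neither follows. For a true 0.35 rise, the shift is 0.035 at E = 0.90 and 0.07 at E = 0.80, about one third and two thirds of the 0.104 standard error.
- **The correction may exist elsewhere.** RGP is to follow a cited method (reference 27) that is not available here, and only a heading and a blood total survive under Protocol 1, where a sampling table may have stood. The assay list does not say that PAH is measured only in arterial blood. This limits certainty about intent, but neither possibility replaces the written formula and assay list, which contain no correction.
- **Change in E with drug or cohort is conjecture.** Correct: the documents give no evidence of it. Nor do they give a way to rule it out. Because allocation is 2:1 within each cohort, a cohort difference in E would not confound the pooled arm comparison, but it would distort an NGT versus T2DM comparison of RGP.

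**Conclusion.** The point holds as a statement about one error. Followed as written, the plan multiplies RGP by the PAH extraction ratio and adds (1 − E) × RGP to HGP. For an assumed E of 0.80 to 0.95, a true even split of the 0.70 mg/kg.min rise reads as 40% to 47.5% kidney. Total EGP is unaffected, and so is the test of zero renal effect when E is constant. What is affected is the size of the renal effect and the kidney/liver apportionment, with a possible differential error if E moves with drug or cohort. The result assumes steady-state PAH balance. The combined direction with the plasma/whole-blood mismatch cannot be settled from the documents. This is a cheap improvement, not a fault that invalidates the design.

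**What to change.** - Assay PAH in the renal vein samples already scheduled, at least at the five baseline times and in the last hour (180, 200, 220 and 240 min): nine assays per subject. All times would need 17 (5 + 12).
- Compute E per subject before and after drug, and set RPF = period PAH clearance / E for each of the two urine periods. Two periods give two flow values per subject; they cannot give an excretion-based flow at each 20-minute point or for the last hour alone. Applying a last-hour E to the 10 AM to 2 PM clearance assumes E is stable over those four hours; assaying across the period removes that assumption.
- Report RGP and HGP from uncorrected clearance as a sensitivity analysis.
- In the same revision, put glucose and flow on the same basis (both plasma or both whole blood, with the conversion stated), so that correcting E alone does not overshoot.
- If the cited method already includes an extraction correction, write it into the formula and the assay list.

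The cost is some extra PAH assays and a small plasma volume, with no new procedure. Check the volume against the 500 ml ceiling in Risk Benefit: Protocol 1 shows 404 ml and the OGTT 45.5 ml. If these add, the total is 449.5 ml, leaving 50.5 ml before any screening blood not already counted.
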